6.5.2.1 Key Secondary Endpoint Analysis (if applicable)

Not applicable.

6.5.2.2 Derivation of Endpoints

BMI will be derived as follows:

```
BMI (kg/m^2) = weight [kg] / (height [m])^2
```

LVMI will be derived using the following formulas:

LVM (g) =
$$0.8 \times [1.04 \times \{(LVDd + IVSTd + PWTd)^3 - LVDd^3\}] + 0.6$$
,

where:

- LVDd is left ventricular internal diameter (diastolic) (cm),
- IVSTd is intraventricular septum thickness (diastolic) (cm),
- PWTd is posterior wall thickness (diastolic) (cm)

TAK675-3001	
Statistical Analysis Plan Amendment 1	

Page 19 of 27 1-Feb-2024

LVM indexed to height (LVMI) = LVM/height^{2.7} (g/m^{2.7}),

where height is measured in meter (m).

The height measurement at baseline will be used to derive LVMI at all timepoints for subjects ≥ 18 years. For subjects < 18 years, the height measurement closest to the LVMI assessment will be used to derive LVMI.

6.5.2.3 Main Analytical Approach

Not applicable.

6.5.2.4 Sensitivity Analysis

Longitudinal data (eGFR, urine protein/creatinine ratio, lyso-Gb3, LVMI and LVEF) will be analyzed using a mixed-effects model for repeated measures (MMRM), using the PP set.

6.5.2.5 Supplementary Analyses

Not applicable.

6.5.3 Other Secondary Endpoints Analysis (if applicable)

Not applicable.

6.5.4 Subgroup Analyses (if applicable)

Efficacy data will be split by age group (2 to <12, 12 to <18, <18, \geq 18 years at Informed Consent). Lyso-Gb3 data will be split by age group (2 to <12, 12 to <18, <18, \geq 18 years at Informed Consent, Total).

6.6 Safety Analysis

The primary analysis will be the incidence of serious TEAEs.

Serious adverse events will be coded using the most recent version of Medical Dictionary for Regulatory Activities (MedDRA) coding dictionary. Serious treatment-emergent adverse events (serious TEAEs) will be summarized for overall and by system organ class (SOC) and preferred term (PT). Analysis of AEs will be performed at both subject level and AE level.

Subjects will be counted once per SOC and once per PT. Multiple events of the same type will be combined for each subject and, when doing this, the worst drug relationship, severity or outcome for each event type will be presented for the analysis. When calculating event rates, the denominator will be the total population size, irrespective of dropouts over the course of follow-up.

TAK675-3001	Page 20 of 27
Statistical Analysis Plan Amendment 1	1-Feb-2024

All summaries of AE and antibody data will be split by age group (2 to <12, 12 to <18, <18, \geq 18 years at Informed Consent, Total).

The safety set will be used.

6.6.1 Adverse Events

Secondary safety analysis

The secondary safety analyses will be based on the safety set.

Adverse events will be coded using the most recent version of Medical Dictionary for Regulatory Activities (MedDRA) coding dictionary. A treatment-emergent adverse event (TEAE) is defined as any event emerging or manifesting at or after the initiation of treatment with an investigational product or medicinal product or any existing event that worsens in either intensity or frequency following exposure to the investigational product or medicinal product until the end of the safety follow-up period (14 days (+7 days) after the last infusion). Treatment-emergent adverse events (TEAEs) will be summarized for overall and by SOC and PT. Analysis of AEs will be performed at both subject level and AE level. Similar displays will be provided for IRRs. An IRR will be defined as an AE that 1) begins either during or within 24 hours after the start of the infusion and 2) is judged as related to study drug. The AEs will be summarized by severity, seriousness, and relation to investigational product.

Subjects will be counted once per SOC and once per PT. Multiple events of the same type will be combined for each subject and, when doing this, the worst severity or outcome for each event type will be presented for the analysis. When calculating event rates, the denominator will be the total population size, irrespective of dropouts over the course of follow-up.

All-cause mortality will be listed by subject. Two listings will be created – one listing the cause of death. The other listing will show serious TEAEs leading to death.

6.6.2 Adverse Events of Special Interest (if applicable)

Infusion-related reactions (IRRs) will be summarized in a similar fashion as overall TEAEs – see Section 6.6.1 above. An additional summary table will be provided for the potential relationship between IRRs and anti-agalsidase alfa antibody status. This summary table will include the specific IRR, the outcome of the IRR, and the antibody status (positive / negative).

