- vADA samples will be collected at baseline visit and evaluation visits prior to infusion; any samples that are confirmed positive for ADA will also be tested for neutralizing antibodies. The test will be performed in the Takeda-designated central laboratory.
- \*Plasma lyso-Gb3 will be assessed in the Takeda-designated central laboratory.
- x An early morning spot urine sample will be obtained to measure protein and creatinine levels. Measurement of urine protein/creatinine ratio will be performed as part of urinalysis (see Appendix 2 for details on urinalysis).
- yTests for hepatitis B surface antigen with confirmation by hepatitis B viral DNA load, HCV antibody with confirmation by HCV ribonucleic acid polymerase chain reaction testing, and human immunodeficiency virus antibody will be performed in the local laboratory.

Sampling time points a Pre-infusion Durin		During infusion	End of Infusion	Post-infusion					
(from start of infusion)	0 min	20 mins	40 mins	50 mins	60 mins	90 mins	120 mins	240 mins	360 mins
Window		±1 min	$\pm 1 \min$	±2 mins	±2 mins	±2 mins	±2 mins	±2 mins	±3 mins
≥18 years old	•	•	•	•	•	•	•	•	•
<18 years old	•		•	•	• ~	A •	•	•	•

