Data collected in clinical trials to-date indicate that REPLAGAL remains safe and well-tolerated during long-term use. As with other intravenously (IV) administered protein therapeutics, the identified and potential risks of treatment with REPLAGAL include occurrence of infusion-related reactions (IRRs), cardiac ischemic events and arrhythmias triggered by IRRs, and potential development of neutralizing antibodies (NAbs) that may compromise efficacy. Of these, IRRs are idiosyncratic and allergic-type hypersensitivity reactions which may be defined as any new signs or symptoms experienced by subjects during the infusion or any new events occurring on the first day of administration of pharmacologic or biologic agents. Infusion-related reactions are the most commonly observed adverse drug reactions associated with REPLAGAL and generally occur within the first 2 to 4 months after initiation of treatment with REPLAGAL. The clinical experience has indicated that IRRs can be mitigated with a combination of infusion-rate control and medications such as antihistamines, antipyretics or low-dose corticosteroids. Cardiac ischemic events and arrhythmias triggered by IRRs have been also reported as risks associated with REPLAGAL treatment in patients with pre-existing cardiac manifestations of Fabry disease. The majority of these events were mild in severity, nonserious, and resolved. Cardiac events triggered by IRRs are possibly due to the hemodynamic stress caused by infusion. Additionally,

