The antibody status, including binding antibody (BAb) and neutralizing antibody (NAb) status, will be summarized as categorical variable by positive and negative at baseline, by transient positive and persistent positive during the study period, and by treatment-induced positive and treatment-boosted positive at each post baseline visits. The antibody titer will be summarized as continuous variable at baseline, and by any positive, by treatment-induced positive and treatment-boosted positive each post baseline visits. *Antibody data, including* BAbs and *NAbs, will also be presented in the form of individual subject listings.*

Antibody status (including binding antibody and neutralizing antibody status) will be defined as follows:

- treatment-induced positive: pretreatment is negative, post treatment become positive
- treatment-boosted positive: pretreatment is positive, post treatment Ab titer increases ≥ 4 folds compared to pretreatment
- persistent positive: at least positive two times (>16 weeks), including last time point tested, or positive at last timepoint tested

TAK675-3001	Page 22 of 27
Statistical Analysis Plan Amendment 1	1-Feb-2024

• transient positive: at least tested positive once, last time point tested is negative

Below are more details regarding the definitions provided above:

- Treatment-induced positive: baseline negative and at least one post-baseline positive
- Treatment-boosted positive: at least one post-treatment positive with Ab titer increases ≥ 4 folds compared to pre-treatment
- Persistent and transient positive: baseline not necessarily negative
- Persistent positive: the duration between first and last post-treatment positive > 16 weeks. The last post-treatment will be the last time point tested.
- Persistent positive: This also include only if the last time point tested positive, regardless of outcome of previous tests.
- Transient positive: at least one post-treatment positive, but last time point tested is negative
- Transient positive exclude the subjects that fulfilled the condition of persistent positive.

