9.2 Data Handling Conventions

9.2.1 General Data Reporting Conventions

Means and medians will be presented to 1 more decimal place than the recorded data. The standard deviations (SDs) will be presented to 2 more decimal places than the recorded data. CIs will be presented using the same number of decimal places as the parameter estimate. When the original data have 3 or more decimal places, the same rule as for 3 decimal places would apply to all.

For categorical variables, the count (n) and percent (%) will be displayed. Unless otherwise stated in table shells, the denominator for percentages is N (the number of subjects in the treatment group within that analysis set). For any summary by subgroups (e.g. by sex), the denominator is the number of subjects in that subgroup/treatment group within that analysis set.

- Percentages will be reported to 1 decimal place, except when the percentage equals exactly 100 where it will be displayed as an integer (100). For zero, only count and no percentage will be displayed.
- For summaries of categorical variables percentages are usually based on N as stated above. However, if missing is not a category then the denominator is the number of subjects with non-missing values. Any exceptions to the denominator should be explained in the footnotes.

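### The planned IRR-by-antibody table (SAP 6.6.2) names only IRR events and an undated antibody status, so as specified it shows the antibody mix among IRRs, not IRR incidence by antibody status

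*SAP*

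**What the plan says.** SAP 6.6.2 states the purpose: "An additional summary table will be provided for the potential relationship between IRRs and anti-agalsidase alfa antibody status". It then names the contents: "This summary table will include the specific IRR, the outcome of the IRR, and the antibody status (positive / negative". It names no IRR-free subjects, no denominator by antibody status and no date at which status is read. It does not say whether binding (BAb) or neutralizing (NAb) antibody is meant.

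Neighbouring sections do not fill the gap explicitly:

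- SAP 6.6.1, on event rates: "the denominator will be the total population size, irrespective of dropouts over the course of follow-up".
- SAP 6.6, on splits: "All summaries of AE and antibody data will be split by age group". Antibody status is not a planned split.
- SAP 9.2.1, general rule: "For any summary by subgroups (e.g. by sex), the denominator is the number of subjects in that subgroup/treatment group within that analysis set". Antibody status is not named as a subgroup.
- SAP 6.6.3 summarises antibody status "by positive and negative at baseline, by transient positive and persistent positive during the study period", and by treatment-induced or treatment-boosted positivity at each post-baseline visit. None of these is tied to IRR onset. By-subject antibody listings are planned.

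On timing, footnote v to Table 1 of the Protocol says: "ADA samples will be collected at baseline visit and evaluation visits prior to infusion". The evaluation visits are Weeks 8, 16, 28, 40 and 52. Protocol 2.2 says IRRs "generally occur within the first 2 to 4 months after initiation of treatment with REPLAGAL". Protocol 6.6.1 adds an antibody sample before the next infusion when a subject has 3 further IRRs despite premedication.

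**The concern.** To show a relationship, IRR occurrence has to be compared between antibody-positive and antibody-negative subjects. A table built only from IRRs gives the reverse proportion: of the reactions seen, how many were in positive subjects. That figure cannot be interpreted without knowing how common positivity is in the whole safety set.

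The undated status is a second gap. Antibody status can change over 52 weeks, and IRRs are expected early. Status at the last sample before the reaction, at the next sample after it, or at any time in the study can classify the same IRR differently. If the choice is made after the data are seen, the result is open to selection.

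Protocol 2.4 names IRRs and immunogenicity among the main identified risks, and this is the only planned table that links them. It should answer its own question without reconstruction.

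**Working it through.** The documents give no figure for this table, and the 20 subjects rest on feasibility, so there is no calculation to reproduce. Three checks were made.

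**1. Effect of the missing denominator.** N = 20 is from SAP 4.0. The IRR counts are assumed for illustration: 4 subjects with an IRR, a = 3 positive and c = 1 negative. Let P be the number of positive subjects among the 20, which the table does not report. Then

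risk ratio = (a / P) ÷ (c / (N − P)).

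| P of 20 | IRR risk, positive | IRR risk, negative | Risk ratio |
|---|---|---|---|
| 3 | 3/3 = 1.00 | 1/17 = 0.06 | 17.0 |
| 5 | 3/5 = 0.60 | 1/15 = 0.07 | 9.0 |
| 8 | 3/8 = 0.38 | 1/12 = 0.08 | 4.5 |
| 10 | 3/10 = 0.30 | 1/10 = 0.10 | 3.0 |
| 15 | 3/15 = 0.20 | 1/5 = 0.20 | 1.0 |
| 18 | 3/18 = 0.17 | 1/2 = 0.50 | 0.33 |

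The IRR-only table is the same in every row. Neither the size nor the direction of the relationship can be read from it alone.

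**2. Sampling against infusions.** Every-other-week dosing at Weeks 0, 2, …, 52 gives 52/2 + 1 = 27 nominal infusions per subject. Five (Weeks 8, 16, 28, 40, 52) fall at a visit with a scheduled antibody sample, and 27 − 5 = 22 do not. Four (Weeks 0, 2, 4, 6) come before the first post-baseline sample. Four months is 4 × 30.4375 / 7 = 17.4 weeks (month length as in SAP 6.6.4). That span holds nine infusions (Weeks 0 to 16), of which two (Weeks 8 and 16) have a scheduled sample at the visit.

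A hypothetical subject shows the effect: an IRR at Week 4, negative at baseline and at Week 8, first positive at Week 28. The last result before the IRR is negative, the first after it is negative, and status at any post-baseline test is positive. SAP 6.6.2 does not say which applies.

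**3. What the other outputs supply.** Under the SAP 6.6.3 definitions, persistent positive covers anyone positive at the last test, and transient positive covers anyone with a post-treatment positive whose last test is negative. Persistent plus transient therefore counts every subject positive at any post-baseline test, which is P on that definition. The listings then allow each subject with an IRR to be placed in a two-by-two table. The comparison can be rebuilt, but the table intended to show it does not provide it.

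**The case against.** A reader might infer that the plan cannot show the relationship at all. The documents do not support that. Saying what the table will include does not make the list exhaustive. SAP 9.2.1 refers to table shells, which are not among the documents, and its subgroup rule would give by-status denominators if status were made the column split. Check 3 shows that the denominator can be recovered from SAP 6.6.3, and with about 20 subjects the listings hide little. All of this stands. The point is limited to the table as SAP 6.6.2 words it: that section does not make antibody status a column split, and SAP 6.6.1 points to the whole population as denominator.

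A reader might also infer that an early IRR will be reported against an antibody first detected months later. That follows only if status means positive at any time, which SAP 6.6.2 does not say. The text is ambiguous; a misclassification is not shown.

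The scheduled samples are also not the whole picture, since the IRR-triggered samples of Protocol 6.6.1 bear directly on this question. They help with timing, but subjects with repeated IRRs may be tested more often and so have more chances of a positive result. The SAP gives no rule for using them in this table.

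Finally, SAP 3.1 tests no hypothesis, and this is one supplementary safety display. That limits the weight of the point but does not remove it.

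**Conclusion.** The point holds in limited form. As specified, the SAP 6.6.2 table gives the antibody mix among IRRs, with status at no stated time, and not IRR incidence by antibody status. In the illustration one such table fits risk ratios from 17 down to 0.33. That range rests on assumed counts (4 subjects with an IRR, 3 of them positive, among 20) and shows what is left undetermined; it does not predict the trial's result. The timing check uses the nominal schedule without missed or shifted infusions. The conclusion also assumes that the unseen table shells do not already add the missing elements.

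No data are lost, the display is descriptive, and the primary serious-TEAE analysis is unaffected. This is a worthwhile, low-cost improvement to a secondary safety output.

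**What to change.** Amend SAP 6.6.2 as follows.

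1. In the safety set, tabulate subjects with at least one IRR and with none, as n/N by antibody status, for BAb and NAb separately. Define positive as positive at any post-baseline test, and show baseline status separately.
2. For each IRR, show the antibody result of the last sample on or before onset and of the first sample after it, including the IRR-triggered samples in Protocol 6.6.1. The order of IRR and seroconversion is then visible, which item 1 alone does not show.
3. State in a footnote that subjects with repeated IRRs may be tested more often.

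A pooled IRR rate per infusion by last prior antibody status is best left out, or shown only within time periods, for example before and after Week 16. The infusions at Weeks 0 to 6 would all carry the baseline value while IRRs are expected early, so a pooled rate would mix antibody status with time on treatment.

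The cost is SAP wording and table programming, using data already collected. Cell counts will be small with about 20 subjects, so the n/N figures should be read descriptively.

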6.6.3 Other Safety Analysis (if applicable)

Tabular summaries of other safety endpoints (eg, vital signs, blood tests, concomitant medications [coded using the World Health Organization Drug Dictionary], anti-agalsidase alfa antibody status, and infusion information) will be produced at baseline and, if applicable, for each postbaseline visit.

Changes in the results of physical examination from the baseline will be presented by visit and body system in the form of a shift table.

TAK675-3001	Page 21 of 27
Statistical Analysis Plan Amendment 1	1-Feb-2024

The observed values and the change from baseline for ECG parameters (PR, QRS, QT, QTc, and heart rate) will be summarized by visit. The number of subjects with normal and abnormal ECG results during the study period will be summarized by visit in the form of a shift table.

Laboratory data will be listed by subject. Subjects with newly occurring abnormalities outside the normal range will be flagged, listed separately, and summarized. The mean change from baseline in laboratory values or a shift table also will be provided at each visit. Change from baseline will be calculated by subtracting the baseline value from the post-baseline value.

Vital sign data will be listed by subject. Mean changes from baseline for vital sign data will be summarized. Subjects with notable abnormal values will be identified and listed separately along with their values – notable abnormal values will only be identified in adult (\geq 18 years) according to the following thresholds:

Sitting and supine		alia
Systolic BP (mmHg)	High and increase	\geq 140 and increase of \geq 20 from baseline value
	Low and decrease	<90 and decrease of >20 from baseline value
Diastolic BP (mmHg)	High and increase	\geq 90 and increase of >15 from baseline value
	Low and decrease	50 and decrease of >15 from baseline value
Pulse rate (bpm)	High and increase	\geq 100 and increase of >15 from baseline value
	Low and decrease	<45 and decrease of >15 from baseline value

The number and percentage of subjects reporting at least one use of concomitant medication during the study will be reported.

The antibody status, including binding antibody (BAb) and neutralizing antibody (NAb) status, will be summarized as categorical variable by positive and negative at baseline, by transient positive and persistent positive during the study period, and by treatment-induced positive and treatment-boosted positive at each post baseline visits. The antibody titer will be summarized as continuous variable at baseline, and by any positive, by treatment-induced positive and treatment-boosted positive each post baseline visits. *Antibody data, including* BAbs and *NAbs, will also be presented in the form of individual subject listings.*

Antibody status (including binding antibody and neutralizing antibody status) will be defined as follows:

- treatment-induced positive: pretreatment is negative, post treatment become positive
- treatment-boosted positive: pretreatment is positive, post treatment Ab titer increases ≥ 4 folds compared to pretreatment
- persistent positive: at least positive two times (>16 weeks), including last time point tested, or positive at last timepoint tested

TAK675-3001	Page 22 of 27
Statistical Analysis Plan Amendment 1	1-Feb-2024

• transient positive: at least tested positive once, last time point tested is negative

Below are more details regarding the definitions provided above:

- Treatment-induced positive: baseline negative and at least one post-baseline positive
- Treatment-boosted positive: at least one post-treatment positive with Ab titer increases ≥ 4 folds compared to pre-treatment
- Persistent and transient positive: baseline not necessarily negative
- Persistent positive: the duration between first and last post-treatment positive > 16 weeks. The last post-treatment will be the last time point tested.
- Persistent positive: This also include only if the last time point tested positive, regardless of outcome of previous tests.
- Transient positive: at least one post-treatment positive, but last time point tested is negative
- Transient positive exclude the subjects that fulfilled the condition of persistent positive.

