### 9.6 Safety Analyses

Adverse events will be coded using the most recent version of Medical Dictionary for Regulatory Activities coding dictionary. Treatment-emergent AEs will be summarized for overall and by system organ class (SOC) and preferred term (PT). Analysis of AEs will be performed at both subject level and AE level. Similar displays will be provided for IRRs. The AEs will be summarized by severity, seriousness, and relation to investigational product.

Subjects will be counted once per SOC and once per PT. Multiple events of the same type will be combined for each subject and, when doing this, the worst severity or outcome for each event type will be presented for the analysis. When calculating event rates, the denominator will be the total population size, irrespective of dropouts over the course of follow-up.

Tabular summaries of other safety endpoints (eg, vital signs, blood tests, concomitant medications [coded using the World Health Organization Drug Dictionary], anti-agalsidase alfa antibody status, and infusion information) will be produced at baseline and, if applicable, for each post-baseline visit.

Changes in the results of physical examination from the baseline will be presented by visit and body system in the form of a shift table.

The observed values and the change from baseline for ECG parameters (PR, QRS, QT, QTc, and heart rate) will be summarized by visit. The number of subjects with normal and abnormal ECG results during the study period will be summarized by visit in the form of a shift table.

Laboratory data will be listed by subject. Subjects with newly occurring abnormalities outside the normal range will be flagged, listed separately, and summarized. The mean change from baseline in laboratory values or a shift table also will be provided at each visit. Change from baseline will be calculated by subtracting the baseline value from the post-baseline value.

Vital sign data will be listed by subject, and any newly occurring changes outside the reference range from baseline will be flagged. Mean changes from baseline for vital sign data will be summarized. Subjects with notable abnormal values will be identified and listed separately along with their values.

The number and percentage of subjects reporting at least one use of concomitant medication during the study will be reported. Subject listings will be provided describing the reason(s) for study discontinuation.

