2.0 STUDY DESIGN

This is a China-only, Phase 3, multicenter, nonrandomized, open-label, single-arm study to evaluate the safety, efficacy, and PK of REPLAGAL in treatment-naïve Chinese subjects with Fabry disease. The study will consist of EOW treatment with 0.2 mg/kg IV infusion of REPLAGAL for up to 52 weeks. A total of 20 safety evaluable subjects aged \geq 7 to \leq 65 years are planned to be enrolled with at least 25% of the total eligible subjects in the age range of \geq 7 to <18 years old.

The study will include a screening period, a baseline visit period, a treatment period, and a safety follow-up period. Screening assessments will occur from Week -7 through Week -2. Baseline visit period will be at Week -1. After completion of baseline procedures and assessments, eligible subjects will receive 0.2 mg/kg IV infusions of REPLAGAL EOW (±4 days) from Day 1 (Week 0) up to Week 52 (end of treatment [EOT] visit) during the treatment period.

Evaluation visits will be performed at clinical site at Week 8 (± 4 days), Week 16 (± 4 days), Week 28 (± 4 days), Week 40 (± 7 days), and Week 52 (± 7 days). Additionally, PK assessments will occur at Day 1 (Week 0) and Week 28 (± 4 days). In order to ensure subjects' safety, subjects will undergo a follow-up period of approximately 14 days (± 7 days) after the completion of the treatment infusion (or the last infusion for early treatment discontinued subjects).

In the event a monitor cannot visit the site in a timely manner due to the coronavirus disease (COVID-19) pandemic, alternative monitoring approaches such as remote source data verification or telephone contact may be used to ensure data quality and integrity and maintain subject safety. Alternative monitoring approaches should be used only where allowed by the local Health Authority and permitted by the institutional review board (IRB)/ethics committee (EC), if applicable.

Safety assessments include monitoring of AEs, use of concomitant medication, clinical laboratory values, vital signs, antibody formation, physical examination, and ECG.

Efficacy assessments include measurements of eGFR, urine protein/creatine ratio, and Brief Pain Inventory (BPI). For pediatric subjects (<18 years old at screening), additional assessment for hearing will be performed.

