4.0 SAMPLE-SIZE DETERMINATION

A sample size of 20 safety evaluable subjects (safety analysis set) is planned to be enrolled in this study to descriptively provide an estimate of the serious TEAE rate. No formal sample size calculations have been done and the sample size is based on feasibility.

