8.0 CHANGES TO PROTOCOL PLANNED ANALYSES

Not applicable.

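### The SAP drops the protocol's out-of-range flag for vital signs and limits notable values to adults, leaving children (at least 5 of 20) with no pre-specified identification of abnormal vital signs

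*SAP*

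**What the plan says.** Protocol 9.6, repeated in the synopsis, plans a by-subject listing and mean changes for vital signs, plus two outputs that pick out individual abnormalities. The first is that "any newly occurring changes outside the reference range from baseline will be flagged". The second is that "Subjects with notable abnormal values will be identified and listed separately along with their values". Neither carries an age limit, and the protocol gives no thresholds for a notable value.

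SAP 6.6.3 keeps the listing and the means: "Vital sign data will be listed by subject. Mean changes from baseline for vital sign data will be summarized". The flag that stands between these two items in the protocol is missing. The notable-value output is kept, but "notable abnormal values will only be identified in adult" subjects (18 years and over), using a table of thresholds for systolic pressure, diastolic pressure and pulse. No rule is given for younger subjects.

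For laboratory data, the same SAP section keeps the corresponding rule: "Subjects with newly occurring abnormalities outside the normal range will be flagged, listed separately, and summarized".

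Under "8.0 CHANGES TO PROTOCOL PLANNED ANALYSES" the SAP states only that the item does not apply.

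**The concern.** Vital signs are a named secondary safety endpoint for all subjects (Protocol Table 4; SAP 1.2.2.1). Protocol 2.2 describes infusion-related reactions as the most common adverse drug reactions to the product and suggests that cardiac events triggered by them may reflect hemodynamic stress from the infusion. Protocol 8.2.3.3 times vital-sign readings before, during and after infusion.

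A programmed rule for abnormal values is the only planned output that picks out individual excursions without depending on the investigator's judgment. If it is withdrawn for one age group, an excursion in a child comes to attention only if the investigator records it as an adverse event or someone finds it in the listing. A reader of the study report who relies on SAP 8.0 would not learn that a protocol-planned output had been dropped.

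**Working it through.** There is no sample-size or power figure to reproduce: the 20 subjects rest on feasibility (SAP 4.0). The check compares the two texts and then counts who is affected.

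**Step 1. Rules that identify an abnormal vital sign.** The four signs collected are those in Protocol 8.2.3.3.

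| Vital sign | Protocol 9.6, any age | SAP 6.6.3, 18 and over | SAP 6.6.3, under 18 |
|---|---|---|---|
| Blood pressure | flag; notable values | notable values, with thresholds | none |
| Pulse | flag; notable values | notable values, with thresholds | none |
| Respiratory rate | flag; notable values | none | none |
| Temperature | flag; notable values | none | none |

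Two gaps follow. Under 18, no sign has a rule. In adults, two of the four signs have none, because the threshold table covers only blood pressure and pulse and the flag that would have covered the rest is gone.

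**Step 2. How many subjects.**
- Planned size: "A sample size of 20 safety evaluable subjects (safety analysis set) is planned to be enrolled" (SAP 4.0).
- Pediatric share: "with at least 25% of the total eligible subjects in the age range of" 7 to under 18 years (SAP 2.0).
- Minimum children: 0.25 × 20 = 5. Maximum adults: 20 − 5 = 15.

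The SAP's identification rule therefore reaches at most 15 of 20 subjects. Restoring the flag would reach all 20.

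**Step 3. What still covers children.**
- The by-subject listing, the tabular summaries at each visit and the mean changes (SAP 6.6.3).
- The investigator's assessment of whether a change from baseline is clinically significant and is an adverse event (Protocol 8.2.3.3).
- Adverse-event and infusion-related-reaction displays (SAP 6.6.1, 6.6.2), with adverse-event summaries split by age (SAP 6.6).

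The age split in SAP 6.6 names adverse-event and antibody data, and that in SAP 6.5.4 names efficacy data. Neither names vital signs, so pediatric vital-sign means may be pooled with adult ones.

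**Step 4. How many pediatric measurement sets, as a range.** Infusions every 2 weeks from Week 0 to Week 52 give 52/2 + 1 = 27. Protocol Table 5 has 4 time points per infusion, 2 of them after it. The post-infusion readings may be omitted, at the investigator's discretion, if the first 3 infusions pass without a reaction.
- No omissions: 5 × 27 × 4 = 540.
- Always omitted after the third infusion: 5 × (3 × 4 + 24 × 2) = 5 × 60 = 300.

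So the range is roughly 300 to 540 sets for 5 children who receive every infusion. It falls with missed infusions or dropout; Protocol 6.5 assumes 10% to 20% dropout.

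**The case against.** The best defense is that the SAP was right not to apply adult cut-offs to subjects aged 7 to 17, and that Protocol 9.1 leaves statistical methods and definitions to the SAP. The protocol's flag was also not ready to run: the documents supply no vital-sign reference range for any age, and Protocol 8.2.3.4 provides for ranges only for laboratory tests. The study is descriptive, tests no hypothesis (SAP 3.1), and has serious treatment-emergent adverse events as its primary endpoint. All values are collected and listed, so a flag could be added later without loss of data. With about five children, a reader can go through the listing by eye.

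Much of this stands. Restricting the adult thresholds to adults is reasonable, and the consequence is limited. But the lack of a range source is a reason to name one, or to declare that the flag is being dropped. It does not justify silent removal while the laboratory flag is kept in the same section. Nor is the adverse-event route an equivalent screen: it depends on a judgment of clinical significance and, for an infusion-related reaction, on a judgment of relatedness as well (Protocol Appendix 3.1).

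Two stronger readings are tempting and are not supported. A reader might infer that children have no vital-sign analysis at all; the listings, visit summaries, mean changes and adverse-event route show otherwise. A reader might also take 540 as the number of pediatric measurement sets with no check of any kind. That figure is a ceiling, and the investigator still assesses changes from baseline.

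**Conclusion.** The concern holds as a departure of the SAP from the protocol that is not declared. At least 5 of 20 subjects have no pre-specified identification of abnormal values on a named secondary safety endpoint, and respiratory rate and temperature have none at any age. The 5 assumes that the planned 20 are enrolled at the 25% minimum; more children would mean more subjects affected. The conclusion does not depend on the count of measurement sets.

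The primary endpoint is untouched and no data are lost. This should be corrected because the output was planned, the group affected is a whole age stratum, and the correction is cheap. It does not threaten the study's main result.

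**What to change.** - In SAP 6.6.3, restore the protocol's flag for values newly outside the reference range, for all subjects and all four vital signs.
- Name the source of the ranges, with age-appropriate ranges for subjects under 18. The documents supply none, so the sponsor must choose and cite them.
- Mark flagged pediatric values in the by-subject listing. Protocol 9.6 asks for a flag on vital signs, not for the separate listing and summary that it requires for laboratory abnormalities, so marking is enough.
- Keep the adult threshold table as it is.
- In SAP 8.0, declare that notable values are restricted to adults, and give the reason.

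The cost is SAP wording, a range look-up and some extra programming. No new data are needed. The small downside is having to select and defend a range source.
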